## 2 STUDY RATIONALE

VTE is one of the leading causes of maternal morbidity and mortality. In efforts to decrease rates of VTE, there is an increased emphasis on administering pharmacologic thromboprophylaxis for antepartum patients with prolonged hospitalizations. Due to physiological changes of pregnancy that may alter the metabolism of unfractionated heparin, it is suspected that dosing of pharmacologic thromboprophylaxis may need to be altered. ACOG's current recommendation is to consider gestational age-based dosing of unfractionated heparin for hospitalized pregnant patients rather than standard dosing. However, there are no prior studies assessing the potential effects of higher dosing. Potential effects of higher dosing include limited receipt of neuraxial anesthesia, increased administration of general anesthesia, delayed time to delivery, and increased bleeding risk. We propose this study to provide a direct comparison of gestational age-based unfractionated heparin dosing to standard dosing of unfractionated heparin for pharmacologic thromboprophylaxis of hospitalized antepartum patients.

For our primary objective, we hypothesize that compared to standard dosing, gestational age-based dosing for VTE prophylaxis is associated with higher rates of elevated aPTT values, a surrogate marker of ineligibility for neuraxial anesthesia. For our additional exploratory objectives, we hypothesize that there will be no significant difference in achieving goal anti-Xa levels (0.2-0.5 IU/mL) between standard dosing and gestational age-based dosing and that particular characteristics (e.g., increased eGFR and higher BMI) are associated with elevated aPTT values with unfractionated heparin administration.

ACOG Practice Bulletin No.123. Thromboembolism in Pregnancy. *Obstet Gynecol* 2011;118:718-729.

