### **11.2 Demographic and Baseline Characteristics**

The following demographic variables will be collected at screening: age, height and weight, body mass index, race, ethnicity. The following baseline characteristics will be collected at screening: gestational age at randomization, gravida, parity, maternal comorbidities.

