### **11.4 Analysis of Secondary Endpoints**

Comparison of maternal demographics, baseline characteristics, additional maternal outcomes, and neonatal outcomes between the two groups will be analyzed using Student's t-test for parametric data, Wilcoxon signed-rank test for nonparametric data, and Chi-squared or Fisher's exact test for comparison of proportions. Descriptive statistics will be performed to summarize which dose resulted in a normal aPTT value and anti-Xa within goal range. Multivariate logistic regression analysis will be performed to determine which factors were associated with an elevated aPTT value. Statistical significance will be set at a p-value of  $< 0.05$  or 95% confidence interval not overlapping.

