### **11.5 Sample Size and Randomization**

Based on an informal/pilot review of antepartum admissions at our institution receiving gestational age-based dosing of unfractionated heparin, 40% of patients and an elevated aPTT

value. Assuming 40% of patients receiving gestational age-based dosing and 3% receiving standard dosing had elevated serum aPTT values, a sample size of 18 women in each dosing group would have 80% power (alpha = 0.05) to demonstrate a significant difference in our primary outcome of evaluating the proportion of women with elevated aPTT values after heparin administration. We increased the sample size by 25% to account for post-randomization drop-out or lab sampling errors. We plan to recruit 46 patients.

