Title of Study: Heparin Prophylaxis Dosing for Antepartum Hospitalizations (HEPDOSE)

NCT Number: NCT04635839

Document Date: June 27, 2022

Document: Statistical Analysis Plan

Traditional univariate analysis was performed for our primary and secondary outcomes with Chi-square or Fisher exact test for categorical variable and t-test or Wilcoxon rank-sum test for continuous variables. A logistic regression analysis was performed to further assess the association of elevated aPTT with gestational age-based dosing of unfractionated heparin relative to standard dosing. We also performed a multivariate logistic regression to adjust for confounders. Confounders included in the model were a priori covariates that potentially could affect the response to unfractionated heparin along with baseline characteristics from our univariate analyses comparing study arm groups that had a p value < 0.2. Via a stepwise regression, none of the variable demonstrated a significant effect on our primary outcome. However, for our final model we elected to adjust for creatinine and obesity based on clinical relevance and a priori knowledge of these factors being potential confounders that may not have been detected in our study cohort due to the small sample size.

Statistical significance was defined as a p-value of < 0.05 or non-overlapping 95% confidence intervals (CI). All analyses were conducted using Statistical Analysis Software (SAS), version 9.4 (Copyright 2013, SAS Institute, Inc. Cary, NC).

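### The final logistic model adjusts for an undefined obesity term although BMI is collected; if that term is a yes/no split, the exploratory BMI association loses power, while the arm comparison hardly changes (minor).

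*SAP*

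**What the plan says.** The SAP describes two logistic analyses of elevated aPTT: one for dosing arm alone, and one with covariates. Of the second it says "We also performed a multivariate logistic regression to adjust for confounders". It reports that stepwise selection found no covariate with a significant effect, and then: "for our final model we elected to adjust for creatinine and obesity based on clinical relevance". It gives no cut-off for obesity, no number of levels, and no reason for using obesity in place of BMI.

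The protocol bears on this in four places:

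- Section 11.2 lists the demographic variables taken at screening: "age, height and weight, body mass index, race, ethnicity".
- Section 2 states, as an exploratory hypothesis, that "particular characteristics (e.g., increased eGFR and higher BMI) are associated with elevated aPTT values".
- Section 3.2(a) makes it a secondary objective to assess which maternal characteristics go with elevated aPTT.
- Section 11.4 assigns that task to a regression: "Multivariate logistic regression analysis will be performed to determine which factors were associated with an elevated aPTT value".

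**The concern.** The hypothesis is graded (more BMI, more risk) and BMI is in the database, yet the covariate named in the final model is a category. If obesity is entered as yes/no, two women just either side of the cut-off are treated as different, and all women on one side of it as alike. When risk rises steadily with BMI, that discards information.

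This is separate from how covariates are selected: it concerns the form in which one covariate enters, and a better selection rule would leave it as it is. What is at stake is the chance of detecting a BMI association under objective 3.2(a). The SAP itself puts its null covariate findings down partly to the small cohort, so avoidable loss of power matters somewhat here.

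**Working it through.** **Inputs from the documents.** Section 11.5 of the protocol gives the event rates: "Assuming 40% of patients receiving gestational age-based dosing and 3% receiving standard dosing had elevated serum aPTT values". It also gives 18 women per arm for 80% power at alpha 0.05, and a planned total of 46. Allocation is 1:1 (section 8.1). I take the test as two-sided, which the protocol does not state.

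**Assumptions, because the documents are silent.** Obesity is a single yes/no term; BMI is roughly normal; its effect is linear on the log-odds scale; 20% to 50% of women are obese.

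**1. The plan's own figure.** The documents give no figure for BMI, so the only one to reproduce is the sample size. The average rate is (0.40 + 0.03)/2 = 0.215.

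n = [1.96 × √(2 × 0.215 × 0.785) + 0.8416 × √(0.40 × 0.60 + 0.03 × 0.97)]² / 0.37² = (1.139 + 0.437)² / 0.1369 ≈ 18.1

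This rounds up to 19 per arm. Power at 18 per arm is 79.7%, so the stated 18 is reproduced to within rounding. Expected events in 46 women are 23 × 0.40 + 23 × 0.03 = 9.9.

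**2. Information kept by one split.** For a linear effect, the share kept is the squared correlation between the variable and its indicator. For a normal variable with a share p above the cut c, this is φ(c)² / [p(1 − p)].

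| Share obese | Kept | Lost | 46 women carry the BMI information of |
|---|---|---|---|
| 50% | 0.3989² / 0.25 = 63.7% | 36.3% | 29.3 |
| 40% | 62.2% | 37.8% | 28.6 |
| 30% | 0.3477² / 0.21 = 57.6% | 42.4% | 26.5 |
| 20% | 0.2800² / 0.16 = 49.0% | 51.0% | 22.5 |

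The shape of the distribution matters. For right-skewed distributions (skewness 0.6 to 1.0, 20% to 60% obese) the loss is about 36% to 47%. For a flat distribution it is 25% at a median split and 37% at 30% obese.

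**3. Power.** I simulated 1,500 trials per setting, with 23 women per arm, marginal event rates of 40% and 3%, and standard normal BMI independent of arm. Likelihood-ratio tests at 0.05 were applied to the BMI term given arm, and to arm given the BMI term. Creatinine was left out.

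| BMI odds ratio per SD | Share obese | BMI term: continuous v yes/no | Arm effect: continuous v yes/no |
|---|---|---|---|
| 1.5 | 30% | 0.16 v 0.12 | 0.945 v 0.949 |
| 1.5 | 50% | 0.18 v 0.13 | 0.949 v 0.949 |
| 2.0 | 30% | 0.38 v 0.26 | 0.959 v 0.957 |
| 2.0 | 50% | 0.37 v 0.26 | 0.954 v 0.947 |
| 3.0 | 30% | 0.70 v 0.48 | 0.959 v 0.951 |
| 3.0 | 50% | 0.66 v 0.48 | 0.965 v 0.956 |

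The simulation error on each power figure is at most √(0.25/1500) = 0.013. A repeat run at 30% obese gave about 0.38 v 0.25 and 0.68 v 0.48 for odds ratios of 2.0 and 3.0.

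**The case against.** **The coding is inferred.** A reader might take it as established that the SAP dichotomised BMI. It does not say so, and obesity classes are not ruled out. Yes/no is only the natural reading. What can be shown from the text is that the term is undefined. Nothing suggests that creatinine was categorised either.

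**The model may have another job.** The SAP presents the covariate model as adjusting the arm comparison, and power to detect a BMI coefficient is not the test of an adjustment covariate. The SAP does not list the variables offered to the stepwise procedure, so BMI may have been examined as a continuous variable there. This objection stands in part. However, section 11.4 of the protocol assigns multivariate logistic regression to the search for associated factors, and the SAP describes no other model that does it.

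**The treatment comparison.** A reader might infer that the adjusted arm odds ratio is compromised. The documents do not support that. Arms are randomised, so no systematic BMI imbalance is expected; power for arm moves by less than one point; and the primary analysis in section 11.3 is an unadjusted Chi-squared test.

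**Few events.** With about 10 expected, the BMI association is weakly powered under either coding unless the effect is large. This stands, and it limits what the change can achieve.

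**Linearity is also an assumption.** A straight line and a single step each use one degree of freedom, and neither is a special case of the other. If the true effect were a threshold at the cut-off, the linear term would lose the same share. The case for linearity here is that the hypothesis is worded as a gradient.

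**Conclusion.** The point holds as a minor one. The SAP's final model uses an undefined obesity term where BMI is available and the exploratory hypothesis names higher BMI. If the term is yes/no, the loss of BMI information is 36% to 51% for a normal BMI with 50% down to 20% obese. At 30% obese, power for the BMI term falls by about 12 points at an odds ratio of 2.0 per SD (0.38 to 0.26) and about 22 points at 3.0 (0.70 to 0.48).

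These figures rest on the inferred coding, the assumed BMI shape, a linear log-odds effect, and all 46 recruited women being analysed. The analysis set in section 11.1 may be smaller. It would be tempting to say flatly that more than a third of the information is lost, but the flat-distribution result of 25% shows that this depends on the shape. The sample size, the primary test and the arm comparison are not put in question.

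**What to change.** 1. In the analysis of maternal characteristics (objective 3.2(a)) and in the adjusted model, enter baseline BMI as one continuous linear term.
2. State how obesity was defined: the cut-off, the number of levels, and which weight it is based on.
3. Report the obesity-coded model alongside as a sensitivity analysis. The SAP is written in the past tense and describes that model as already fitted, so it should not be dropped.
4. Label the BMI model as added after the obesity model was fitted.

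The data are already collected, and against a yes/no term the change uses no extra degrees of freedom. The costs are an assumption of linearity on the logit scale, a post hoc change that must be declared, and one more model to report. With about 10 expected events, the BMI estimate should be shown with its confidence interval, and a non-significant result should not be read as absence of an association.

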STATISTICS Primary Analysis Plan	
Analysis of the primary endpoint of whether or not there was an elevation in aPTT in each dosing group will be performed with a Chi-squared test. Multivariate logistic regression analysis will be performed to determine which factors were associated with an elevated aPTT value. Comparison of maternal demographics, baseline characteristics, additional maternal outcomes, and neonatal outcomes between the two groups will be analyzed using Student's t-test for parametric data, Wilcoxon signed-rank test for nonparametric data, and Chi-squared or Fisher's exact test for comparison of proportions. Descriptive statistics will be performed to summarize which dose resulted in a normal aPTT value and anti-Xa within goal range. Statistical significance will be set at a p-value of < 0.05 or 95% confidence interval not overlapping.

Rationale for Number of Subjects	
Assuming 40% of patients receiving gestational age-based dosing and 3% receiving standard dosing have an elevated aPTT value, a sample size of 36 women (18 in each arm) would have 80% power to demonstrate a significant difference between the proportion of women with elevated aPTT values after administration. We plan to recruit 46 (23 in each arm) to account for post-randomization drop out and lab sampling errors.

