### **11.3 Analysis of Primary Endpoint**

Analysis of the primary endpoint of whether or not there was an elevation in aPTT in each dosing group will be performed with a Chi-squared test. Comparison will be considered statistically significant at a p-value of  $< 0.05$ .

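### Non-overlapping 95% confidence intervals serve as an alternative significance criterion: this is not a 5% test, the interval is undefined, and in sparse tables it can override the named test

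*SAP*

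**What the plan says.** The SAP, in its closing paragraph, sets one rule for all analyses: "Statistical significance was defined as a p-value of < 0.05 or non-overlapping 95% confidence intervals (CI"). For the primary and secondary outcomes it allows "Chi-square or Fisher exact test for categorical variable" and does not say which of the two applies when. It also describes logistic regression models.

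The protocol is not uniform. Section 11.3 specifies that "whether or not there was an elevation in aPTT in each dosing group will be performed with a Chi-squared test", and continues "Comparison will be considered statistically significant at a p-value of" below 0.05, with no interval criterion. Section 11.4, which covers secondary endpoints and the multivariable regression, adds "or 95% confidence interval not overlapping". The synopsis has the same clause ("95% confidence interval not overlapping") at the end of a paragraph that opens with the primary analysis.

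Neither document says which intervals are compared, how they are computed, or which criterion governs if the two disagree.

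**The concern.** Three things are wrong with the clause.

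- Comparing two single-arm intervals is a different test from testing the difference, and its error rate is not 5%.
- With few events the answer depends on the interval method, which is left open. This trial expects few events in the standard arm, and none at all is about an even chance.
- A logistic model gives one interval for an odds ratio. There is no second interval for it to overlap; the relevant question is whether it contains 1.

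Because the two criteria are joined by *or*, an interval comparison can supply a claim of significance that the named test does not support. The primary endpoint also has two rules: section 11.3 on one side, the synopsis and SAP on the other.

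**Working it through.** **Inputs.** Section 11.5: "Assuming 40% of patients receiving gestational age-based dosing and 3% receiving standard dosing had elevated serum aPTT values", and "a sample size of 18 women in each dosing group would have 80% power (alpha = 0.05"). Section 11.5 inflates by 25% to 46 in total; the synopsis gives 23 per arm. The sidedness of alpha is not stated; two-sided is assumed. The interval type is not stated, so Wald, Wilson and exact (Clopper-Pearson) intervals were all tried.

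**The plan's own figure.** The pooled normal formula, two-sided and without continuity correction, gives 79.7% power at 18 per arm, which matches the stated 80%. Inflation: 18 × 1.25 = 22.5, rounded up to 23.

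**Non-overlap as a test.** Two 95% intervals fail to overlap when the difference exceeds 1.96(SE1 + SE2). The z-statistic must therefore exceed 1.96(SE1 + SE2)/√(SE1² + SE2²). With equal SEs this is 2 × 1.96/√2 = 2.77, two-sided p = 0.0056. At an SE ratio of 2 the level is 0.0085, and at a ratio of 3 it is 0.0132. Where the z-test has 80% power, non-overlap alone has 51%.

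**Equal arms, chi-squared.** Every possible table was enumerated at 18 + 18 and 23 + 23. For all three interval types, no table had non-overlapping intervals with chi-squared p ≥ 0.05. The *or* rule therefore makes the same decisions as chi-squared alone. Exact power at 40% v 3% is 85.4% (n = 18) and 93.7% (n = 23), and the maximum type I error is 6.5% and 5.4%, each with or without the clause.

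**Equal arms, Fisher.** At the planned rates the smallest expected cell count is 18 × (0.40 + 0.03)/2 = 3.9, or 4.9 with 23 per arm, so Fisher's test is a natural choice. Zero events in the standard arm, where the Wald interval collapses to 0–0%, has probability 0.97^18 = 58%, or 0.97^23 = 50%. Take 4/18 v 0/18:

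- Fisher p = 2 × C(18,4)/C(36,4) = 2 × 3060/58905 = 0.104.
- Chi-squared = 36 × (4 × 18)²/(18 × 18 × 4 × 32) = 4.5, p = 0.034.
- Wald: 3.0–41.4% and 0–0%, no overlap.
- Wilson: 9.0–45.2% and 0–17.6%, overlap.
- Exact: 6.4–47.6% and 0–18.5%, overlap.

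Under Fisher plus the *or* clause, this table is significant with Wald intervals and not significant with the other two. At 40% v 3% it has probability 3.5% at n = 18, and the corresponding 4 v 0 table has 0.7% at n = 23. The maximum type I error of Fisher-or-Wald is 3.5% (n = 18) and 3.7% (n = 23), against 2.9% and 2.6% for Fisher alone.

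**Unequal arms.** Section 11.1 restricts the analysis to women with two doses and at least one aPTT, and section 13.3 does not replace those who withdraw from treatment, so the arms may differ in size. As an illustration, take 23 v 18, with 4/23 v 0/18:

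- Chi-squared = 41 × (4 × 18)²/(23 × 18 × 4 × 37) = 3.47, p = 0.063.
- Fisher p = [C(23,4) + C(18,4)]/C(41,4) = (8855 + 3060)/101270 = 0.118.
- Wald: 1.9–32.9% and 0–0%, no overlap. Wilson and exact intervals overlap.

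With both true rates 10%, chi-squared rejects in 4.5% of trials at these sizes. The 4 v 0 table adds C(23,4) × 0.1⁴ × 0.9³⁷ = 8855 × 0.0001 × 0.0203 = 1.8%, giving 6.3%. Fisher alone rejects in 1.4%. The Wald clause adds the 4 v 0 table (1.8%) and the 5 v 0 table (C(23,5) × 0.1⁵ × 0.9³⁶ = 0.8%), giving about 4.0%.

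**The case against.** The strongest reply is that *or* means either criterion suffices, that non-overlap is the stricter one, and that the clause is therefore redundant. For equal arms and chi-squared, the only test section 11.3 names for the primary endpoint, this is correct in every table checked. The exceptions need Wald intervals, which no document names, together with Fisher's test or unequal arms, and they are confined to a few sparse tables.

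The wording may also be loose. Section 11.4 uses the singular, directly after the regression sentence, so the authors may have meant a contrast interval that excludes its null value. That would be close to the p-value rule, but neither document says so.

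Two stronger readings are tempting, and the documents do not support them.

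- A reader might infer that the rule makes the same data both significant and not significant. It does not: p < 0.05 with overlapping intervals is simply significant under *or*. What remains open is which interval is meant.
- A reader might infer a large loss of power. At 18 per arm and 40% v 3%, non-overlap alone has 30% power with exact intervals and 46% with Wilson intervals, but the plan never uses that criterion alone. The disagreement in that direction (chi-squared p < 0.05 with overlapping exact intervals in 55% of such trials at n = 18 and 38% at n = 23) matters only to someone who judges by the intervals alone.

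**Conclusion.** The concern holds in a limited form. The plan gives an alternative significance criterion that is not a 5% test, does not define its interval, cannot be applied to a single odds ratio, and is inconsistent with section 11.3 for the primary endpoint. For equal arms of 18 or 23 with chi-squared, its effect on decisions is nil. With Fisher's test or unequal arms it can turn a non-significant sparse table into a significant one, but only if Wald intervals are used.

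General inflation of the type I error should not be inferred. The rise from 4.5% to 6.3% belongs to one illustrative setting (23 v 18, both rates 10%, chi-squared plus Wald); with Fisher the rate there stays below 5%. The maximum of 6.5% for chi-squared at 18 per arm is present without the clause. These results assume two-sided tests, uncorrected Pearson chi-squared and per-arm intervals. The sparse secondary comparisons under section 11.4 are the most exposed, since there the protocol itself applies the two-part rule.

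**What to change.** Delete the non-overlap criterion from the synopsis, section 11.4 and the SAP. Declare significance only from the two-sided p-value of the named test, and say whether chi-squared or Fisher applies to each comparison. Report one 95% interval for the between-arm contrast, read against 0 for differences and against 1 for ratios. For the primary endpoint this should be a score-type risk-difference interval such as Newcombe or Miettinen-Nurminen, which does not collapse when an arm has no events.

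Because the SAP is written in the past tense, also confirm that no reported significance rests on an interval comparison. The cost is a sentence or two in each document; no further data or patients are needed.
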